The Children's Oncology Group has received a Certificate of Confidentiality from the federal government, which will help us protect the privacy of our research subjects. The Certificate protects against the involuntary release of information about subjects collected during the course of our covered studies. The researchers involved in the studies cannot be forced to disclose the identity or any information collected in the study in any legal proceedings at the federal, state, or local level, regardless of whether they are criminal, administrative, or legislative proceedings. However, the subject or the researcher may choose to voluntarily disclose the protected information under certain circumstances. For example, if the subject or his/her guardian requests the release of information in writing, the Certificate does not protect against that voluntary disclosure. Furthermore, federal agencies may review our records under limited circumstances, such as a DHHS request for information for an audit or program evaluation or an FDA request under the Food, Drug and Cosmetics Act.

The Certificate of Confidentiality will not protect against mandatory disclosure by the researchers of information on suspected child abuse, reportable communicable diseases, and/or possible threat of harm to self or others.

ABSTRACT

This subprotocol is a component of the Pediatric MATCH trial APEC1621. The APEC1621SC screening protocol details the process used to identify actionable mutations in patient tumor samples which will determine eligibility for this subprotocol. This is a phase 2 trial of tipifarnib in children with relapsed or refractory solid tumors (including lymphomas, histiocytoses and CNS) harboring specified activating mutations in the HRAS gene.

Tipifarnib will be administered with food at mg/m²/dose PO BID (maximum 600 mg/dose) for 7 days followed by 7 day rest period, alternating on a 28 day cycle. Eligibility for this trial includes a relapsed or refractory pediatric solid tumor that harbors an activating mutation in *HRAS* (at codons G12, G13, Q61, or A146), as determined by the Pediatric-MATCH screening protocol, APEC1621SC. The trial's primary objective is to determine the antitumor activity of tipifarnib, using objective response rate (CR +PR) as a primary endpoint. Secondary objectives include ongoing assessment of tipifarnib-associated toxicities.

EXPERIMENTAL DESIGN SCHEMA

Treatment Schedule Table			

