2.5 Overview of Proposed Pediatric Study

This is a phase 2 trial of tipifarnib in children with recurrent or refractory solid tumors, CNS tumors, non-Hodgkin lymphomas and histiocytic disorders harboring specific activating mutations in HRAS.

Doses of up to 300mg/m²/dose twice daily for 21 out of 28 days have been previously tolerated in children. This is equal to a total dose of 12,600mg/m² per cycle. Although the MTD in adults for the 7 day on/ 7 day off schedule was not determined, the current RP2D for adults is 600mg/dose twice daily on a 7 day on/ 7 day off schedule (total dose of 16,800 mg/ cycle; equal to ~9,700mg/m²/cycle, and therefore less than the cumulative cycle doses previously deemed safe in children). The pediatric dose of the current adult RP2D is mg/m²/dose twice daily mg/m²/cycle) and therefore, also less than doses previously deemed safe in children, and therefore will serve as the recommended dose for the pediatric MATCH trial.

Tipifarnib will be administered at mg/m²/dose by mouth twice daily for 7 days on followed by 7 days off alternating on a 28 day cycle (i.e., days 1-7 and 15-21 of a 28 day cycle).

The primary aim of this trial will be to establish the objective response rate to tipifarnib. While there will not be multiple pre-determined mutation-based cohorts, responses will be analyzed retrospectively with respect to specific HRAS mutations and variant allele frequency.

Key secondary objectives include further evaluation of the tolerability of tipifarnib in pediatric patients. Toxicity will be assessed using CTCAE V5.0. Imaging for disease evaluation will occur every other cycle x 3, then every three cycles. Disease response will

be assessed according to RECIST v1.1 for solid tumors and 2-dimensional measurement for CNS tumors.

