- Tumor Disease Evaluation should be obtained on the next consecutive cycle after initial documentation of either a PR or CR. Subsequent scans may restart 2 cycles after the confirmatory scan. If the institutional investigator determines that the patient has progressed based on clinical or laboratory evidence, he/she may opt not to confirm this finding radiographically.
- 4-A Neurological exam also required for CNS patients.
- 4-B Non- Hodgkin Lymphoma/ Histiocytosis patients are required to have PET scans within 2 weeks prior to start of therapy and should also be followed with PET scans if positive at diagnosis. Refer to Section 12.8
- Patients with neuroblastoma must have both CT/MRI and MIBG scintigraphy prior to the start of protocol therapy if the patient was enrolled with or has a history of having MIBG avid tumor. Otherwise the patient must have either FDG-PET/CT or PET/MR prior to the start of protocol therapy. For patients with neuroblastoma and measurable disease by CT or MRI, lesions should be measured and followed using the same modality (CT or MRI) in addition to MIBG or FDG-PET/CT. For patients with neuroblastoma and evaluable disease by MIBG scintigraphy, use the same modality (MIBG scintigraphy) to image and follow patients; CT/MRI are not required but may be performed as clinically indicated. Refer to Section 12.5 and Section 12.8:
- Bone marrow aspirate and/or biopsy only required in patients suspected of having bone marrow metastasis on the basis of history, symptoms, laboratory evaluation or other clinical data.
- Bone marrow aspirate and/or biopsy should be performed only when complete response or partial response is identified in target disease or when progression in bone marrow is suspected.
- 7. The medication diary should be collected and reviewed weekly during cycle 1 (medication). The medication diary should also be reviewed after completion of each treatment cycle and uploaded into RAVE.

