- 12.3.3.6 Cytology, Histology: These techniques can be used to differentiate between partial responses (PR) and complete responses (CR) in rare cases (e.g., residual lesions in tumor types, such as germ cell tumors, where known residual benign tumors can remain).
 - Cytology should be obtained if an effusion appears or worsens during treatment when the measurable tumor has met criteria for response or stable disease.
- 12.3.3.7 FDG-PET: While FDG-PET response assessments need additional study, it is sometimes reasonable to incorporate the use of FDG-PET scanning to complement CT scanning in assessment of progression (particularly possible 'new' disease). New lesions on the basis of FDG-PET imaging can be identified according to the following algorithm:
 - a. Negative FDG-PET at baseline, with a positive FDG-PET at followup is a sign of PD based on a new lesion.
 - b. No FDG-PET at baseline and a positive FDG-PET at follow-up: If the positive FDG-PET at follow-up corresponds to a new site of disease confirmed by CT, this is PD. If the positive FDG-PET at follow-up is not confirmed as a new site of disease on CT, additional

follow-up CT scans are needed to determine if there is truly progression occurring at that site (if so, the date of PD will be the date of the initial abnormal FDG-PET scan). If the positive FDG-PET at follow-up corresponds to a pre-existing site of disease on CT that is not progressing on the basis of the anatomic images, this is not PD.

Note: A 'positive' FDG-PET scan lesion means one that is FDG avid with an uptake greater than twice that of the surrounding tissue on the attenuation corrected image.

For patients with a positive PET scan at diagnosis, PET can be used to follow response in addition to a CT scan using the International Pediatric non-Hodgkin Lymphoma Response Criteria. 55

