12.7.2 Evaluation of Measurable Disease

Complete Response (CR)

Disappearance of all disease. CT or MRI should be free of residual mass or evidence of new disease. FDG-PET should be negative.

Complete Response Unconfirmed (CRu)

Residual mass is negative by FDG-PET; no new lesions by imaging examination; no new and/or progressive disease elsewhere

Partial Response (PR)

50% decrease in SPD (the sum of the products of the largest diameter and the perpendicular diameter for a tumor mass) on CT or MRI; FDG-PET may be positive (Deauville score or 4 or 5 with reduced lesional uptake compared with baseline); no new and/or PD; morphologic evidence of disease may be present in BM if present at diagnosis; however, there should be 50% reduction in percentage of lymphoma cells.

No Response (Stable Disease)

Neither sufficient shrinkage to qualify for PR nor sufficient increase to qualify for PD, taking as reference the smallest sum diameters while on study.

Progressive disease

For those with > 25% increase in SPD on CT or MRI, Deauville score 4 or 5 on FDG-PET with increase in lesional uptake from baseline, or development of new morphologic evidence of disease in BM

12.7.3 Evaluation of Non-measured Lesions (CT-based response, PET/CT based response not applicable)⁵⁹

Complete Response (CR): Absent non-measured lesions.

Partial response (PR): Absent/normal, regressed, lesions, but no increase.

Stable Disease (SD): No increase consistent with progression

Progressive Disease (PD): New or clear progression of preexisting

non-measured lesions.

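### Two lymphoma/histiocytosis conditions, residual marrow disease under PR and the trigger for follow-up PET, are tied to status at diagnosis instead of the pre-treatment baseline

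*Combined protocol and SAP*

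**What the plan says.** Section 2.5 describes the population as "children with recurrent or refractory solid tumors, CNS tumors, non-Hodgkin lymphomas and histiocytic disorders".

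**Marrow.** Under PR in Section 12.7.2, "morphologic evidence of disease may be present in BM if present at diagnosis", provided that the percentage of lymphoma cells is reduced by 50%. No reference time is given for that reduction.

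**PET.** Footnote 4-B to the Section 8.1 schedule states that these "patients are required to have PET scans within 2 weeks prior to start of therapy", and that they "should also be followed with PET scans if positive at diagnosis". Section 12.3.3.7 repeats the trigger in permissive form: "For patients with a positive PET scan at diagnosis, PET can be used to follow response in addition to a CT scan". Section 12.7.2 uses on-study PET in several places:
- For CR, "FDG-PET should be negative".
- CRu needs a PET-negative residual mass.
- PR allows a positive PET "with reduced lesional uptake compared with baseline".
- One route to PD is a rise in uptake from baseline.

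**Elsewhere.** Appendix VI (therapy delivery map for subsequent cycles, item h) limits repeat marrow examination to patients with known involvement at baseline. Section 8.2.1 lists the prestudy baseline and the end-of-cycle disease evaluations as the material for central review. Footnote 4-B points to Section 12.8, which is Best Response. The lymphoma/histiocytosis criteria are in Section 12.7.

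**The concern.** In newly diagnosed patients, diagnosis and baseline coincide and the wording would be harmless. Here they can be far apart, and marrow or PET status may have changed in between.

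The marrow condition acts directly on the primary endpoint. ORR counts CR and PR, and the condition can refuse PR to a patient whose nodal disease and marrow have both improved on treatment.

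The PET condition acts on data collection. It can leave a patient without the scan that CR, CRu or PET-based progression calls for, even though a comparable pre-treatment scan exists.

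A responder must also be confirmed by central review (Sections 11.5 and 12.3.1.1). Diagnosis-era evaluations are not on the list of material submitted for it, so that package does not let the reviewers check a condition that depends on diagnosis.

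**Working it through.** **Step 1. Where diagnosis enters the rules.** Each part of Section 12.7.2, and the PET triggers, sorted by time reference:

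| Rule | Reference point |
|---|---|
| CR | None: no residual mass, PET negative |
| CRu | On-study PET; no earlier reference |
| PR, PET uptake | Baseline |
| PR, residual marrow disease allowed | **Diagnosis** |
| PR, 50% fall in marrow lymphoma cells | Not stated |
| SD, size | Smallest sum on study |
| PD, PET uptake | Baseline |
| PD, marrow | New disease; diagnosis not mentioned |
| Follow-up PET (footnote 4-B; 12.3.3.7) | **Diagnosis** |

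Diagnosis therefore governs one condition within PR and the trigger for follow-up PET.

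**Step 2. Marrow condition, for a patient who otherwise meets PR.**

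| Marrow at diagnosis | At entry | On study | PR as written | PR with a baseline anchor |
|---|---|---|---|---|
| Involved | Involved | Down by at least 50%, not clear | Allowed | Allowed |
| Clear | Involved | Down by at least 50%, not clear | **Not met** | Allowed |
| Any | Involved | Cleared | Condition not needed | Condition not needed |
| Involved | Clear | Positive again | Barred: PR requires no new or progressive disease | Barred |

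Only the second row changes. The first row also needs a reference time for the 50% reduction, which the text does not supply.

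**Step 3. PET trigger.**

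| PET at diagnosis | Pre-treatment PET | Follow-up PET required by 4-B | With a baseline trigger |
|---|---|---|---|
| Positive | Positive | Yes | Yes |
| Negative or not done | Positive | **No** | Yes |
| Positive | Negative | Yes | No |

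In the second row, CR, CRu and PET-based PD may lack a required scan. PR does not need one: it rests on a 50% fall in the sum of products on CT or MRI, and a positive PET is compatible with it. A patient whose disease shrinks enough on CT or MRI still counts in ORR. The Section 1.1 definition of ORR does not name CRu.

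**Step 4. Design figures (Section 11.3).** Inputs: N = 20, success at 3 or more responses, null rate 5%, target rate 25%. With X binomial, P(X ≥ 3) = 1 − P(0) − P(1) − P(2).
- At 5%: 1 − (0.3585 + 0.3774 + 0.1887) = 0.0755, within the stated 10% ceiling.
- At 25%: 1 − (0.0032 + 0.0211 + 0.0669) = 0.9087, against the stated 90%.

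The plan's figures are reproduced. None depends on the wording at issue, so none changes with the fix.

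**The case against.** **Diagnosis may be loose wording for study entry.** This is possible, but the text does not define it so, and the protocol separates the two elsewhere. Solid-tumour CR refers to markers at study enrolment (12.4.1), the relative Curie score to trial entry (12.5.1), and the PET parts of 12.7.2 to baseline. Appendix VI, with its baseline condition for repeat marrow, tells sites when to repeat the marrow. It does not change the PR definition.

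**A trigger is not a prohibition.** Nothing forbids follow-up PET in other patients. Section 12.3.3 asks for the same method at baseline and follow-up, and the CR rule itself calls for a negative PET. This stands. The PET wording creates a risk of missing scans, not a certainty.

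**Progression would still be found.** Every patient has scheduled disease evaluation, growth above 25% on CT or MRI is PD, clinical progression is accepted, and local calls count as PFS events. This also stands. Some PET-only progression could be called later, but nothing shows a material lengthening of PFS.

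**Few patients are affected.** The paediatric HRAS mutations that Section 2.1.1 assigns to a histology are in rhabdomyosarcoma, ectomesenchymoma and neuroblastoma. None is assigned to lymphoma or histiocytosis, although both are eligible, and non-Hodgkin lymphoma and Langerhans cell histiocytosis are listed in Appendix VII for expansion. The number is probably small, but the documents do not give it.

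**Conclusion.** The point holds in a limited form. The PR marrow condition is mis-anchored and, read literally, would classify one kind of responder as a non-responder. The PET trigger disregards the mandatory pre-treatment scan and can leave CR, CRu and PET-based PD without data, but it does not by itself remove a CT- or MRI-based PR from ORR. Only lymphoma/histiocytosis patients whose marrow or PET status changed between diagnosis and entry are affected.

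Three stronger readings may tempt a reader, and the documents support none of them:
- **That CR, PR and PD as a whole are judged against the wrong reference.** Uptake for PR and PD is compared with baseline, CR is absolute, and the PD marrow rule does not mention diagnosis.
- **That marrow involved at diagnosis, clear at entry and positive again on study is PR and PD at once.** PR excludes new or progressive disease, so there is no such conflict.
- **That the trial loses a calculable amount of power.** This would need a count of affected patients, which the plan does not give. It would also have to treat them as unable to respond, which does not follow for the PET condition.

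The conclusion assumes that diagnosis carries its ordinary meaning of original diagnosis.

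**What to change.** 1. **Section 12.7.2, PR.** Make residual marrow disease acceptable if it was present at study baseline, and state that the 50% reduction in lymphoma cells is relative to baseline.
2. **Footnote 4-B and Section 12.3.3.7.** Tie follow-up PET to a positive pre-treatment PET. Both places must change, or the protocol will contradict itself.
3. **Footnote 4-B.** Point to Section 12.7 instead of 12.8. Section 12.3 carries the same numbering slip for lymphoma/histiocytosis and can be corrected at the same time.

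The cost is wording only. The pre-treatment PET is already mandatory, and Section 8.1 already calls for a pre-study marrow examination where involvement is suspected. The small downside is that some baseline-PET-positive patients will have follow-up PET who would not under the literal text. Patients positive at diagnosis but negative at entry would no longer be required to have it. Sample size, alpha, power and the decision rule stay as they are.

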8.2 Radiology Studies

8.2.1 Central Radiology Review for Response: Patients who respond (CR, PR) to therapy or have long term stable disease (SD) (≥ 6 cycles) on protocol therapy will be centrally reviewed. The Operations center will notify the site when a patient has met the criteria for review. The tumor disease evaluations to be submitted for review include baseline (prestudy) evaluations as well as all end of cycle tumor disease evaluations which occurred while the patient was on the subprotocol therapy study

8.2.2 Technical Details of Submission:

To ensure an adequate interpretation of FDG-PET and CT with contrast scans, scans transferred between the treating institutions and the Imaging and Radiation Oncology Core Group IROC RI (QARC) must be submitted in Digital Imaging and Communications in Medicine (DICOM) format. BMP files, JPG files, or hard copies (films) are unacceptable for adequate interpretation of PET and CT with contrast scans. Imaging studies must be submitted electronically as outlined in the following paragraph. The images will be made available to study radiologists and nuclear medicine physicians for central review. Submission of Diagnostic Imaging data in DICOM format is required.

Alternatively, the images and reports may be submitted via sFTP to IROC Rhode Island. Digital data submission instructions including instructions for obtaining a sFTP account, can be found at http://irocri.qarc.org. Follow the link labeled digital data. Sites using the Dicommunicator software to submit imaging may continue

to use that application.

Corresponding Radiology reports may be submitted along with the electronic submission via sFTP or may be emailed to [contact]. The COG operations center and IROC are available to assist with any queries regarding the corresponding radiology reports which should be included when the scans are submitted

Questions may be directed to [contact] or [contact].

IROC Rhode Island (formerly QARC) will facilitate the central reviews.

For FDG-PET imaging, the transferred imaging data should include uncorrected and attenuation-corrected PET projection data, as well as the reconstructed PET or PET/CT images used by the institution to achieve a response assessment. If low-dose CT was used for attenuation correction, the acquired CT images should also be submitted. The imaging data submitted for central review must allow the study to be reconstructed and displayed in transaxial, sagittal and coronal formats using standard reconstruction techniques. Reconstructed MPEG clips and similar types of reconstructions will not be accepted. CT and MRI images similarly should be submitted in a format that either includes properly reconstructed multi-planar viewing formats in soft tissue and bone windows, or includes the thin-section axial acquisition data from which multi-planar reconstructions can be re-created.

Sites not able to submit imaging electronically may submit imaging via CD. CD's may be sent by courier to:

Address for submission: IROC RI (QARC)

[figure not shown]
[name]

[name]

[name] [contact] [contact] Web: http://irocri.garc.org

8.3.1

9.0 **AGENT INFORMATION**

9.1 **Tipifarnib** (12/22/2021) (R115777, Zarnestra®)

9.1.1 Source and Pharmacology:

Tipifarnib is a potent and selective nonpeptidomimetic inhibitor of farnesyltranferase (FTI) both in vitro and in vivo. Its mechanism of action seems to be in the context of angiogenesis inhibition, induction of apoptosis and direct antiproliferative effects. FTIs have consistently shown high activity in HRAS mutated tumor cell lines.

9.1.1.1 Pharmacokinetics (PK)

Tipifarnib is rapidly absorbed after oral administration with Cmax observed within 2 to 4 hours after dosing. From population PK analyses, the absolute bioavailability of tipifarnib under fed conditions is 29.3% in cancer patients. Concomitant intake of a high fat meal increases the extent of absorption by an average of 26.8% compared with administration under fasting conditions. The PK profile of tipifarnib is consistent with a 3-compartment disposition model, with an initial fast distribution half-life (alpha) of about 36 minutes, followed by a dominant elimination half-life (beta) of about 2.4 hours, and a slower terminal half-life (gamma) of about 19 hours. Tipifarnib does not accumulate with multiple dosing. Linear PK are observed for tablets over the dose range of 100 mg through 600 mg. The steady-state volume of distribution following i.v. administration to cancer patients is 169 L. The binding of tipifarnib to plasma proteins is extensive, mostly to albumin and to a lesser extent alpha-1 acid glycoprotein and is not dependent on tipifarnib concentrations.

Tipifarnib is extensively metabolized following oral administration. Little or no tipifarnib is excreted unchanged in the urine. Less than 6% of the initial dose is recovered in feces as the parent compound. Approximately 14.4% of the administered dose is excreted in the urine as tipifarnib-glucuronide. The mean Cmax value in plasma was about 95% higher and the mean AUC12h value about 85% higher in subjects with mild hepatic impairment compared to subjects with normal liver function. These results are consistent with its extensive hepatic metabolism as the predominate route of tipifarnib elimination.

9.1.2 **Potential Drug Interactions**

Tipifarnib is a substrate for the CYP450 enzymes (mostly CYP 3A4/5) and UDP-glucuronosyltransferase (UGT). Due to the potential for drug-drug interactions, tipifarnib should not be administered with strong inhibitors or inducers of CYP3A4/5 or UGT. Additionally, CYP 2C19, 2D6, and 2E1 were observed to play a minor role in tipifarnib clearance in human liver microsomes. Population PK trials using different classes of common concomitant medications show that 1) enzyme-inducing antiepileptic drugs can significantly reduce tipifarnib plasma concentrations and 2) antifungal azoles do not alter tipifarnib clearance.

In vitro, tipifarnib inhibited the metabolism of CYP450 enzymes 2C8/9/10, 3A4/5, 2A6, and 2D6. Although the interaction is not likely based on very low unbound concentrations of tipifarnib, the potential for drug-drug interactions between tipifarnib and drugs metabolized by these enzymes cannot be excluded. Patients should not receive concomitant medication with sensitive or narrow therapeutic range substrates of these CYP isoforms while receiving tipifarnib.

Tipifarnib is extensively bound to blood albumin and is not dependent on drug concentration. Use caution when co-administering with other highly protein-bound drugs with narrow-therapeutic ranges.

Pharmacokinetic trials with tipifarnib and either omeprazole or rabeprazole showed no clinically meaningful effect on tipifarnib exposure. The impact of aluminum or magnesium-containing antacids has not been evaluated.

Patient Care Implications:

Tipifarnib is contraindicated in individuals with hypersensitivities to imidazole-containing agents (e.g. clotrimazole, ketoconazole, miconazole).

Advise women of child-bearing potential and men with female partners of child-bearing potential to use two (2) highly effective forms of contraception 2 weeks prior to starting study treatment, while receiving study treatment and for 1 (one) month after the last dose.

Since tipifarnib could induce toxicity of male reproductive organs and potentially impair fertility, sperm cryopreservation is recommended for men study participants who wish to preserve their fertility following study treatment.

9.1.3 **Toxicity**

The Comprehensive Adverse Event and Potential Risks list (CAEPR) provides a single list of reported and/or potential adverse events (AE) associated with an agent using a uniform presentation of events by body system. In addition to the comprehensive list, a subset, the Specific Protocol Exceptions to Expedited Reporting (SPEER), appears in a separate column and is identified with bold and italicized text. This subset of AEs (SPEER) is a list of events that are protocol specific exceptions to expedited reporting to NCI (except as noted below). Refer to the 'CTEP, NCI Guidelines: Adverse Event Reporting Requirements' http://ctep.cancer.gov/protocolDevelopment/electronic applications/docs/aeguidelines.pd for further clarification. *Frequency is provided based on patients*.

NOTE: Report AEs on the SPEER **ONLY IF** they exceed the grade noted in parentheses next to the AE in the SPEER. If this CAEPR is part of a combination protocol using multiple investigational agents and has an AE listed on different SPEERs, use the lower of the grades to determine if expedited reporting is required.

Note: R115777 (tipifarnib) in combination with other agents could cause an exacerbation of any adverse event currently known to be caused by the other agent, or the combination may result in events never previously associated with either agent.

9.1.4 Formulation and Stability:

Two strengths (100 mg and 300 mg) of film-coated, compressed tablet formulations are provided. The 100 mg tablets are circular and white with a tablet weight of 223.5 mg. The 300 mg tablets are white and capsule-shaped with a tablet weight of 669.5 mg. Tablets are supplied in HDPE bottles containing 45 tablets per bottle.

Tablet formulations have the same qualitative composition. The tablets contain tipifarnib and the following inactive ingredients: lactose monohydrate, maize starch, hypromellose, microcrystalline cellulose, crospovidone, colloidal anhydrous silica, and magnesium stearate. The film coatings contain hypromellose, titanium dioxide, lactose monohydrate, polyethylene glycol, and triacetin. The non-functional film coating is for taste masking purposes.

